14.4.2 Secondary Outcome Measures

- Total, spontaneous, and traumatic ABR, and spontaneous AJBR

For total ABR, spontaneous ABR, traumatic ABR and spontaneous JABR, separate negative binomial models will be used for the second 6 months treatment period (Days 183 to 364) as well as for the complete 12-month treatment period (Days 1 to 364).

The negative binomial model for the bleed rate will include covariates for study arm, stratum, age, and race. The multiple imputations technique will be used for incomplete observation periods as described for the primary endpoints analysis. Subgroups for age and race will be analyzed as well.

For all other outcome measures, descriptive statistics will be presented for the 2 dosing regimens. Point estimates (means and medians) and their 95% CIs will be computed to include:

- Total weight-adjusted consumption of BAX 855 for each prophylactic regimen
- Overall hemostatic efficacy rating at 8 ± 1 h after initiation of treatment and at resolution of bleed
- Number of BAX 855 infusions needed for the treatment of bleeding episodes
- HJHS
- Physical domain and component scores of the SF-36
- Physical Activity Levels

In case of surgeries, descriptive statistics will be performed for the following secondary outcome measures:

- Intra-, post- and perioperative hemostatic efficacy in case of surgery (see Section [22.5.1](#) for details)
- Intra- and postoperative blood loss in case of surgery (see Section [22.5.2](#) for details)

PK parameters before randomization will be summarized descriptively over all subjects to include:

- $AUC_{0-\infty}$, IR at 15-30 minutes post-infusion, $T_{1/2}$, MRT, CL, C_{max} , T_{max} , and V_{ss}

PK parameters after 9 months will be summarized descriptively by prophylactic treatment regimen:

- $AUC_{0-\infty}$, IR at 15-30 minutes post-infusion, $T_{1/2}$, CL, C_{max} , and T_{max}
- IR over time will be displayed as boxplots for the 2 prophylactic regimens

Correlation of VWF:Ag and PK parameters will be assessed by boxplots and Spearman rank correlation coefficient.

Descriptive statistics will be used for the secondary safety outcome measures (see Section [8.4.2.2](#)):

- Occurrence of AEs and SAEs

- Changes in vital signs and clinical laboratory parameters (hematology, clinical chemistry, and lipids)
- Inhibitory antibodies to FVIII, and binding antibodies to FVIII, BAX 855, PEG, and CHO protein

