22.5 Efficacy assessment

22.5.1 Intra-, Post-, and Perioperative Hemostatic Efficacy

The hemostatic efficacy will be assessed at the end of surgery (Table 5), at postoperative day 1 (Table 6), and overall as a perioperative assessment (Table 7).

Table 5 Intraoperative Efficacy Assessment Scale		
	Prior to the discharge from the recovery room, the operating surgeon will assess the intraoperative hemostatic efficacy compared to that expected for the type of procedure performed in a non-hemophilic population	
Rating	Criteria	
Excellent	Intraoperative blood loss was less than or equal to that expected ($\leq 100\%$)	
Good	Intraoperative blood loss was up to 50% more than expected (101-150%)	
Fair	Intraoperative blood loss was more than 50% of that expected ($>150\%$)	
None	Uncontrolled hemorrhage that was the result of inadequate therapeutic response despite proper dosing, necessitating rescue therapy	

Table 6 Postoperative Efficacy Assessment Scale (Postoperative Day 1)		
	On postoperative Day 1, the operating surgeon will assess the postoperative hemostatic efficacy compared to that expected for the type of procedure performed in a non-hemophilic population	
Rating	Criteria	
Excellent	Postoperative blood loss was less than or equal to ($\leq 100\%$) that expected	
Good	Postoperative blood loss was up to 50% more (101-150%) than expected	
Fair	Postoperative blood loss was more than 50% ($>150\%$) of that expected	
None	Significant postoperative bleeding that was the result of inadequate therapeutic response despite proper dosing, necessitating rescue therapy	

Table 7		
Perioperative Efficacy Assessment Scale (at discharge or 14 days post-surgery, whichever is first)		
	At discharge or 14 days post-surgery, whichever is first, a hematologist will assess the perioperative efficacy compared to that expected for the type of procedure performed in a non-hemophilic population	
Rating	Criteria	
Excellent	Perioperative blood loss was less than or equal to (\leq 100%) that expected Required blood components for transfusions were less than or similar to that expected	
Good	Perioperative blood loss was up to 50% more (101-150%) than expected Required blood components for transfusions were less than or similar to that expected	
Fair	Perioperative blood loss was more than 50% of that expected ($>$ 150%) Required blood components transfusions were greater than that expected	

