3.1.2 Secondary Outcome Measures

3.1.2.1 Efficacy

1. Total, spontaneous, and traumatic ABR, and spontaneous AJBR.
2. Total weight-adjusted consumption of BAX 855.
3. Overall hemostatic efficacy rating at 8 (\pm 1) hours after the initiation of treatment and at resolution of bleed.

4. Number of BAX 855 infusions needed for the treatment of bleeding episodes.
5. HJHS.
6. Intra-, post- and perioperative hemostatic efficacy in case of surgery.
7. Intra- and postoperative blood loss in case of surgery.

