4.6 Surgery Analysis Set (SGAS)

The surgery analysis set is to consist of all subjects in the FAS that underwent some form of surgery (including dental) during the course of their PROPEL participation as recorded on the eCRF.

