5.9 Statistical Tests

The default significance level will be 5%; CIs will be 95% and all tests should be two-sided, unless otherwise specified in the description of the particular analysis.

P-values obtained from statistical inference tests should be presented using four decimal places.

Unless otherwise specified the default summary statistics for quantitative variables will be as follows:

- The number of subjects in each category (n).
- Mean.
- Standard deviation (SD).
- First quartile (Q1).
- Median.
- Third quartile (Q3).
- Inter-quartile range (IQR); calculated as $Q3 - Q1$.
- Minimum.
- Maximum.

The number of subjects (n) with missing or unavailable results for quantitative variables will be presented as “Not reported” where applicable. A “Not reported” category should only be presented should there be unavailable results. No distinction based on the reason for unavailable results will be made within any presentations.

If the original data has N decimal places (as derived from the raw data) (i.e., decimal precision [N]), then the summary statistics are to contain the following decimal places (with a maximum of three decimals):

- Minimum and maximum: N.
- Mean, median, Q1, Q3 and IQR: N + 1.
- SD and CI: N + 2.

For qualitative variables the number (n) and percentage (%) of subjects in each category will be the default summary presentation. Unless otherwise specified, percentages should be calculated relative to the total number of subjects in the relevant analysis set and treatment arm as described in the latest version of the Output Templates. For unavailable assessments a “Not reported” category should be presented. A “Not reported” category will only be presented if applicable. The “Not reported” category should be presented with a percentage so that the sum of the percentages of all categories, including the “Not reported” category, totals 100%. No distinction based on the reason for unavailable results will be made in any presentations.

All values should be rounded using the SAS[®] function ROUND. All calculated percentages should be presented using one decimal place.

The following data handling will be applied for PK assessments/analysis.

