7.1.2 Bleeding Episodes

Subject listings will be presented for the following items using the analysis set indicated in brackets:

- Bleeding episodes treated with BAX 855 including efficacy ratings (FAS).
- Bleeding episodes not treated with BAX 855 (FAS).
- Annualized bleeding rate and interval between bleeding episodes (SAS).
- Course of target joints (SAS).
- Magnetic resonance imaging and ultrasound (SAS).

Summary tables will be presented for the following items using the analysis set indicated in brackets:

- Descriptive statistics on annualized bleeding rate (FAS, PPAS) presented by age group, geographical location and race,.
- Comparisons presented by age group and race on:
 - Annualized bleeding rate overall and for the second 6-month study period (FAS and PPAS).
 - Sensitivity Analysis on ABR during the second 6-month study period (FAS).
- Comparisons presented by age group and race on observed annualized bleeding rate (FAS and PPAS).
- Comparisons presented by age group on:
 - Average coagulation parameters against ABR using the Spearman rank correlation coefficient, both overall and for the second 6-month study period (FAS and PPAS).
 - Reduction on ABR (FAS and PPAS).
 - Descriptive statistics on average interval between episodes [Months] (FAS and PPAS).
 - Bleeding episodes (FAS).
 - Hemostatic efficacy against number of BAX 855 infusions to treat perioperative bleeds (FAS).
- Presented by age group, bleed type, bleed severity, bleed location and bleed timing:
- Characteristics of bleeding episodes treated with BAX 855 (FAS).
- Hemostatic efficacy against number of BAX 855 infusions to treat bleeds (FAS).

Figures will be presented for the following items using the FAS:

- Dot and whisker plot (point and 95% CI) of ABR (by treatment arm).
- Multi bar plot of subject treatment profile with infusions, bleeding episodes and antibody titers.
- Linear regression plot of average observed factor VIII trough levels (IU/dL) against observed ABR.
- Linear regression plot of TGA against observed ABR.

The following information items are obtained from the eCRF:

- Bleeding episodes (Bleeding Episode eCRF panels).
- Target joints (Haemophilia A History/Blood Group/Target Joint Identification and Development of new Target Joints eCRF panels).
- Infusions to treat bleeding episodes and prophylactic infusions prior to bleeds (Study Infusion eCRF panels).
- Ultrasound (Ultrasound eCRF panel).

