7.2 Analysis of Secondary Efficacy Outcome Measures

The following secondary efficacy outcome measures are discussed in Section 7.1.2:
Bleeding Episodes:

- Total, Spontaneous, and Injury Related (Traumatic) ABR, and Spontaneous AJBR.
- Overall hemostatic efficacy rating at 8 hours (± 1 hour) after initiation of BAX 855 infusion for the treatment of the bleed as well as at the resolution of the bleed.
- Number of BAX 855 infusions needed for the treatment of bleeding episodes.
- Intra-, post- and perioperative hemostatic efficacy in case of surgery.
- Intra- and postoperative blood loss in case of surgery.

The following are the other secondary efficacy measures that are discussed in this section:

- HJHS questionnaire.
- Haemo-SYM questionnaire.
- Physical domain and component scores of the SF-36 questionnaire.
- EQ-5D questionnaire.
- Healthcare resource utilization (as recorded in the subject diaries).
- Subject physical activity levels.
- The total weight-adjusted consumption of BAX 855 for each treatment arm.

Subject listings will be presented for the following items using the SAS:

- HJHS questionnaire.
- Haemo-SYM questionnaire
- SF-36 questionnaire.
- EQ-5D questionnaire.
- Health resource usage and events.
- Physical activity.

Summary tables containing descriptive statistics and comparisons, using the Wilcoxon signed rank and Mann-Whitney U tests, will be presented on the following items using the FAS:

- The HJHS questionnaire.
- The Haemo-SYM questionnaire.
- The SF-36 questionnaire.
- The EQ-5D questionnaire.
- Health Resource Use.

A summary table containing descriptive statistics only of subject physical activity will also be presented. The summary tables should be presented by age group.

The following information item is obtained from the eCRF:

- Haemophilia joint health score (*Joint score [HJHS] eCRF panel*).

The following information items are obtained from the ERT third party vendor diary data:

- Haemo-SYM item responses and scores.
- SF-36 item responses and scores.
- EQ-5D item responses and scores.
- Health resource utilization.
- Physical activity records.

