7.2.8 Surgery

Subject listings will be presented for the following surgery related items using the SGAS:

- Surgical report.
- Preoperative FVIII substitution plan (including modifications).
- Estimated and observed blood loss (including drain removal blood loss).
- Hemostatic efficacy assessments.
- Drain removal.
- Postoperative prophylaxis.
- Transfusion Requirements.

Summary tables containing descriptive statistics will be presented for surgery related blood loss and transfusion requirements using the SAS by age group.

The following information items are obtained from the eCRF:

- Surgical report information (Surgical Report eCRF panel).
- Preoperative FVIII substitution information (Preoperative FVIII Substitution Plan and Modifications of Preoperative FVIII Substitution Plan eCRF panels).
- Surgery related blood loss (Estimated Blood Loss, Surgical Report and Post-Operative 24 Hours/Drain removal Blood loss eCRF panels).
- Postoperative prophylaxis (Postoperative Prophylaxis eCRF panel).
- Transfusion requirements (Transfusion Requirements eCRF panel).

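### The SAP plans no summary of the surgical haemostatic-efficacy ratings that the protocol promises, and it puts the surgical blood-loss and transfusion tables on the whole safety set instead of its own surgery set

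*SAP*

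**What the plan says.** **Protocol.** Section 8.4.2.1 lists surgical haemostatic efficacy and surgical blood loss as secondary outcomes. Section 14.4.2 commits to an analysis of both: "In case of surgeries, descriptive statistics will be performed for the following secondary outcome measures". It names no analysis set. Section 22.5.1 defines the efficacy outcome: "The hemostatic efficacy will be assessed at the end of surgery (Table 5), at postoperative day 1 (Table 6", followed by an overall perioperative rating at discharge or 14 days (Table 7). Each is a four-level scale from Excellent to None, judged mainly on blood loss against what a patient without haemophilia would be expected to lose.

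**SAP, endpoint and pointer.** Section 3.1.2.1 keeps the endpoint: "Intra-, post- and perioperative hemostatic efficacy in case of surgery". Section 7.2 then assigns it, together with surgical blood loss, to another section: "The following secondary efficacy outcome measures are discussed in Section 7.1.2". The only surgery-related efficacy table in 7.1.2 is "Hemostatic efficacy against number of BAX 855 infusions to treat perioperative bleeds (FAS", on the full analysis set. Section 7.1.2 has no blood-loss analysis.

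**SAP, surgery section.** Section 4.6 defines a dedicated set: "The surgery analysis set is to consist of all subjects in the FAS that underwent some form of surgery". Section 7.2.8 uses it for listings of, among other items, the efficacy ratings, estimated and observed blood loss, and transfusions. For tables it says: "Summary tables containing descriptive statistics will be presented for surgery related blood loss and transfusion requirements using the SAS by age group". The ratings are not among the tabulated items.

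**SAP, denominators.** Section 5.9 sets the default that "percentages should be calculated relative to the total number of subjects in the relevant analysis set and treatment arm". This applies unless otherwise specified and refers to the Output Templates. Section 5.8, which records departures from the protocol's analysis, does not mention surgery.

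**The concern.** There are two separate defects.

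First, a protocol secondary outcome has a promised summary that the SAP does not deliver. A programmer working from the SAP would produce a listing of the ratings and no table. Someone who follows the 7.2 pointer would find a table of perioperative bleeds by number of infusions. As titled, that table is conditioned on treated bleeds, so a procedure rated Excellent with no treated bleed would not appear in it.

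Second, the surgical summary tables rest on a population that mostly had no surgery, while the listings of the same items rest on those who did. Any row expressed as a percentage, such as transfused yes or no, would then describe the trial population and not the surgical patients. The tables would also not reconcile with the listings.

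**Working it through.** **1. The ratings, traced through the plan.**

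| Place | What it provides for the three ratings |
|---|---|
| Protocol 14.4.2 | Descriptive statistics, with reference to 22.5.1 |
| SAP 3.1.2.1 | Retained as a secondary outcome |
| SAP 7.2 | Pointer to 7.1.2 |
| SAP 7.1.2 | No summary of the ratings; one table on perioperative bleeds by infusion count |
| SAP 7.2.8 | Subject listing on the SGAS; no table, and no efficacy panel among the named eCRF sources |
| SAP 5.8 | No change declared |

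The same trace for blood loss ends differently. The pointer to 7.1.2 fails, but 7.2.8 does plan both a listing and a table.

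**2. The analysis set.** By SAP 4.2 the SAS is every enrolled subject with at least one BAX 855 infusion. By SAP 4.6 the SGAS is the subjects in the full analysis set who had surgery, dental included. The SAS therefore contains everyone without surgery, and also subjects who received only the PK infusion.

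**3. Effect on percentage rows.** The documents state no surgical figure, so there is nothing to reproduce. For illustration, let N be the SAS size and k the number of surgery subjects. For e subjects with an event:

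- percentage on the SAS = e/N
- percentage on the SGAS = e/k
- inflation of the denominator = N/k

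Take N = 116, the planned randomised number (Protocol 14.1.1), as a stand-in for the SAS size. Assume k between 3 and 30, and take e = 1.

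| k (assumed) | 1/k | 1/116 | 116/k | (116 − k)/116 |
|---|---|---|---|---|
| 3 | 33.3% | 0.9% | 38.7 | 97.4% |
| 5 | 20.0% | 0.9% | 23.2 | 95.7% |
| 10 | 10.0% | 0.9% | 11.6 | 91.4% |
| 20 | 5.0% | 0.9% | 5.8 | 82.8% |
| 30 | 3.3% | 0.9% | 3.9 | 74.1% |

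The last column is the share of subjects without surgery. SAP 5.9 works per arm. With 58 per arm (Protocol 8.1) and surgeries split evenly, the factor is 58/(k/2) = 116/k, the same as above. In any arm or age group it is the size of that cell divided by the surgery subjects in it.

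**4. Effect on blood loss in mL.** Subjects without surgery have no value, and SAP 5.5 imputes nothing outside bleeding rates, exposure and adverse events. Means, medians and quartiles are therefore the same on either set, except for any SAS subject operated on without being in the full analysis set.

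**The case against.** A reader might infer that the SAP has replaced the surgical endpoint with a different one. The documents do not support that. The endpoint stays in SAP 3.1.2.1, the ratings are listed subject by subject on the SGAS, and nothing says that the perioperative-bleed table stands in for them. That table's scale is not named and perioperative bleed is not defined, so it cannot be called a substitute either. What is missing is a summary, and the pointer is wrong.

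A reader might also infer that surgical results in general are missing or diluted. Blood loss and transfusions are both listed and tabulated, and blood-loss means and medians do not move (step 4). Dilution is confined to percentage rows. It is also conditional: the 5.9 rule is a default, and the Output Templates, which are not among the documents, might restrict the table to surgery subjects. Whether someone without surgery would count as Not reported is likewise not stated. Further, transfusion requirement is not itself a listed secondary outcome; it enters only as a criterion in the Table 7 rating.

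These limits stand. They do not remove the core: a template could narrow a denominator, but the SAP text still names the wrong set for these tables and plans no summary of the ratings. The protocol does not require procedures as the denominator or a major/minor split, so neither is claimed as an error here.

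**Conclusion.** The point holds in a limited form. The SAP falls short of Protocol 14.4.2 by planning a listing of the three surgical ratings and no descriptive summary. Its cross-reference leads to the wrong section for both surgical outcomes, and the departure is not declared. Its blood-loss and transfusion tables use the SAS where its own listings use the SGAS.

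The size of the second defect depends on assumptions. With 3 to 30 surgery subjects among about 116, and the 5.9 default applied, percentage denominators would be about 39 to 4 times too large. The surgery count is unknown, 116 is planned randomisation and not the SAS size, and the Output Templates have not been seen. Continuous blood-loss statistics are essentially unaffected.

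Only descriptive secondary outcomes are involved, probably in few subjects. No hypothesis test depends on them, and the primary comparison is untouched.

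**What to change.** Three edits to the SAP:

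1. In 7.2.8, change the analysis set for the blood-loss and transfusion summary tables from SAS to SGAS.
2. In 7.2.8, add a summary table (n, %) of the Protocol Table 5, 6 and 7 ratings on the SGAS. State whether subjects or procedures are counted, because SAP 5.3.2 foresees more than one surgery per subject.
3. In 7.2, redirect the pointer for surgical haemostatic efficacy and surgical blood loss from 7.1.2 to 7.2.8.

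If a listing of the ratings is all that is intended, 5.8 should say so as a change from the protocol.

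The cost is a few lines of SAP text and one small table. The ratings are already collected under the protocol and already listed, so no new data are needed.

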7.3 Sensitivity Analyses

A sensitivity analysis will be performed on the primary outcome measure as described in Section: 7.1.2: Bleeding Episodes.

8. SAFETY EVALUATION

Safety evaluation results form part of the secondary objectives of this study.

8.1 Adverse Events

Subject listings will be presented for all AEs using the SAS with breakdowns by seriousness and occurrence before of after first infusion of BAX 855. Summary tables of AEs that occurred during of after first infusion BAX 855 will be presented using the SAS including breakdowns by relationship to BAX 855, seriousness and severity.

The following information items are obtained from the eCRF:

- Adverse event details per subject (Adverse Events eCRF panel).
- Date and time of BAX 855 administration (Study Infusions eCRF panels).
- Reason for not completing the study (Study Completion/Termination eCRF panel).

Adverse events are coded using the Medical Dictionary for regulatory activities (MedDRA) as documented in the Data Management documentation at the time of performing the analysis.

The following derivations will be made based of the eCRF reported results:

- AEs are considered to have occurred during or after BAX 855 administration if:
 - The known start date and/or time of the AE is equal to or after the date and/or time of first BAX 855 administration in the current study, which is defined for safety analysis purposes as the PK-infusion for dose determination.
 - The eCRF question “When did event occur in relation to treatment with BAX 855 ?” has a response of any of the following:
 - During PK infusion.
 - Within 24 hours after PK infusion.
 - After more than 24 hours from PK infusion.
 - Before first treatment with BAX 855.
 - During BAX 855 treatment.
 - Within 24 hours after last BAX 855 treatment.
 - After more than 24 hours from last BAX 855 treatment.

- Time since last BAX 855 infusion should be determined as:

$$\textit{Time} = [\textit{Start Date/Time of AE}] - [\textit{Date/Time of Last BAX 855 Infusion}]$$

where the date/time of last BAX 855 exposure is the last possible BAX 855 administration, regardless of reason, prior to the start of the AE. Time since last BAX 855 infusion should only be determined if the full start date (regardless of whether time is known or not) of the AE is known. Time since last BAX 855 infusion will be presented in either hours or days, based on the following criteria:

- Presented in hours if start time of AE is known and time since last BAX 855 infusion is < 24 hours.
 - Presented in days if start time of AE is known and time since last BAX 855 infusion is \geq 24 hours.
 - Presented in days if start time of AE is not known.
- Duration of AE should be determined as:

$$\textit{Duration} = [\textit{End Date/Time of AE}] - [\textit{Start Date/Time of AE}]$$

The duration of an AE will be presented in either hours or days, based on the following criteria:

- Presented in hours if both start time and end time of the AE is known and the duration is < 24 hours.
- Presented in days if both start time and end time of the AE is known and the duration is \geq 24 hours.
- Presented in days if either start time or end time or both are unknown.
- An AE is considered non-serious if the eCRF question “Was AE serious?” is answered “No” and considered serious if the question is answered “Yes”.
- An AE is considered severe if the eCRF question “Severity” is answered “Severe”.
- An AE is considered related as assessed by the Investigator if the AE is indicated as “Possibly related” or “Probably related” in the eCRF. An AE is considered unrelated as assessed by the Investigator if the AE is indicated as “Not related” or “Unlikely related” in the eCRF.
- An AE is considered related as assessed by the Sponsor if the Sponsor Medic deem the AE related to the study medication. Prior to the execution of any

analyses described in this SAP, a list of all AEs in the database will be provided to the Sponsor Medic to assess relationship from a Sponsor perspective of AE to study medication.

- An AE is considered leading to discontinuation of study medication if action taken in BAX 855 is indicated as “Drug withdrawn” in the eCRF.
- An AE is considered leading to discontinuation of study if the AE is indicated as the primary reason why the subject did not complete the study from the Study Completion/Termination eCRF panel.
- An AE is considered as leading to death if the AE outcome is indicated as “Fatal” in the eCRF.
- An AE will be considered an allergic reaction if the question “Was this event considered to be an allergic reaction to Bax 855” is indicated as “Yes”.
- An AE will be considered a thrombotic event if the question “Is this a thrombotic event” is indicated as “Yes” in the eCRF.

Tables should be presented by age group, system organ class (SOC) and PT, the number of subjects who experienced an AE at least once, and the rate of subjects with AE(s).

